6.5.8.3 Hematologic

For grade 2 or higher hematologic toxicities, 5-fluorouracil dose will be reduced by 20% from 1000 to 800 mg/m²/day. For grade 2 or higher hematologic toxicities as a second occurrence, 5-fluorouracil dose will be reduced from 800 to 640 mg/m²/day.

6.5.8.4 Skin

-
In case of rash including hand-foot syndrome or moist desquamation of grade 3 lasting > 7 days or grade 4, the dose of 5-fluorouracil will be reduced by 20% from 1000 mg/m²/day to 800 mg/m²/day in the subsequent cycle.

6.5.8.5 Cardiac

Patients without prior history of angina, who develop angina that appears to be temporarily related to the infusion of 5-FU, must have the drug infusion stopped and the 5-FU permanently discontinued.

6.6 Neck Dissection

A neck dissection should be considered if a palpable or worrisome radiographic abnormality persists in the neck eight weeks after radiotherapy ends.

7.0 Toxicity Measurement

Toxicities will be graded according to the Common Terminology Criteria for Adverse Events, Version 3.0 (CTCAE) (Appendix XI).

8.0 Quality of Life Assessment

In patients with head and neck carcinoma, both the disease and its treatment often significantly impact daily functions and activities such as eating, speaking, and socializing. Radiotherapy, particularly combined with chemotherapy, is associated with severe mucositis, sticky saliva, pain, dry mouth, hoarseness, fatigue, skin irritation, and difficulties in swallowing and tasting. Many of these symptoms can persist years after completion of treatment. Dental problems such as radiation caries could develop. Many of these side effects are the results of photon irradiation to the normal tissues, such as the major salivary glands, adjacent to the tumor.

Proton beam radiation has very distinctive physical properties. The beams can be modulated so that the beam stops at the distal edge of the target, resulting in little or no exit dose. This superior dose distribution, when compared to photons, allows high dose conformality and uniform dose distribution around the target and much lower integral dose to the non-target normal tissue. The impact of proton beam irradiation in the health-related quality of life (QOL) of the head and neck cancer patients has not been studied.

8.1 Self-assessment of quality-of-life

The validated 35-item EORTC-QLQ-H&N questionnaire along with the EORTC QLQ-C30 which measures general quality of life will be used (Appendix IV and V). These self-administrated questionnaires will be given pre-radiation treatment, at approximately 1.5, 3, 6, 12, and 24 months post-treatment.

Patients who are found to have serious concerns in quality of life at any time point will be referred to the appropriate sources accordingly. For patients with severe mucositis and pharyngitis, pain medications will be prescribed. Patients with difficulty swallowing or speech dysfunction will be evaluated by speech and swallowing specialists. Patients who have difficulty maintaining their weights will be referred to the nutritional service; gastrostomy tube for feeding will be placed if indicated. Patients with dental problems will be evaluated by the dental service. For patients with difficulties with body image and social interactions, they will be offered to meet with a social worker to discuss their problems. Psychiatric evaluation will be referred if indicated.

8.2 Objective assessment of swallowing function

Improved locoregional control of advanced head and neck cancer has been reported using concurrent radiotherapy and chemotherapy. Concurrent chemoradiation can result in increased acute and long-term dysphagia compared with radiation alone. Late dysphagia and fibrosis are major factors limiting the intensity of therapeutic regimens for head and neck cancer.

Videofluoroscopic swallowing study (VFSS) (Appendix X) will be used to evaluate swallowing function. VFSS is a validated method of objective assessment of swallowing, allowing viewing and recording of the structures and dynamics of the swallowing process. Each subject will be asked to swallow multiple trials of various food consistencies in varying amounts. The consistencies included thin liquid barium (diluted with water) followed with non-diluted barium, followed with a puree, soft food (fruit mixed with barium), and a solid (shortbread cookie) coated with barium. The examinations are recorded, and analysis of the three phases of swallowing - oral, pharyngeal, and esophageal – is subsequently completed. Assessment will be focused on bolus manipulation and control and bolus passage, including cohesion, motility, and timing.

Evaluation of swallowing function will be performed pre-therapy and at approximately 3, 12, and 24 months after therapy.

8.3 Objective assessment of xerostomia

Sialometry will be performed before initiation of the first radiation fraction, and at approximately 3, 6, 12, and 24 months after the completion of radiation.

8.3.1 Unstimulated Whole Saliva: Patients should refrain from eating, drinking or dental hygiene for at least 60 minutes before collection. During collections, patients should be seated and instructed to minimize orofacial movements and not to attempt to influence salivary flow (such as by sucking or swallowing). Just before the collection, the patient should be instructed to swallow. He/she should then be instructed to allow saliva to accumulate in the floor of mouth for 60 seconds without swallowing. The accumulated saliva should be collected into a pre-weighted container. The patient should repeat this procedure four more times for a total collection time of five minutes. Subjects should be instructed not to swallow during the entire collection procedure.

8.3.2 Stimulated Whole Saliva: After the collection of unstimulated saliva, patients will have 2% citrate solution applied with cotton tipped applicators to the lateral tongue bilaterally five times over a two minute period (0, 30, 60, 90, and 120 seconds). The mouth should then be emptied of retained citrate solution. Saliva should then be collected for five minutes, using the same method as for unstimulated saliva.

8.4 Speech Assessment/Head and Neck Health Status Assessment Inventory (HNHSAI)

Patient self-assessment of speech outcome is an important element in quality-of-life measurements after chemoradiation. Speech assessment questionnaires are from the Head and neck health status assessment inventory (HNHSAI) (14). Nine functional and five attitudinal speech items will be used. The patients' responses to the HNHSAI will be recorded so that the lowest value of 1 represents the most impaired function and the highest value of 5 represents normal or optimal function. "Not applicable" responses are considered appropriate. If the patient responded to the query about problems talking at work with the "not applicable" response (i.e. "I'm not currently employed"), the response will be treated as missing. The speech assessment will be conducted within 14 days of initiation of radiation treatment and at 1.5, 3, 6, 12, and 24 months after treatment completion.

8.5 ChemoSensory Questionnaire (CSQ)

Treatments for head and neck cancer commonly results in smell and taste dysfunction which then can lead to quality-of-life changes. Smell and taste dysfunction can also have a major negative impact on patients' nutrition status.

The Chemosensory Questionnaire (CSQ) developed by Goldberg et al (15) will be used. Four questions each on smell and taste will be used. A minimum score of 4 and a maximum of 20 for the smell scale and taste scale are possible with a higher score indicating better function. If there is a single missing score in a single section, the average of the three remaining scores is used for the missing value. If two questions are missing in a single section, then the survey section is invalid. The chemosensory assessment will be conducted within 14 days of initiation of radiation treatment and at 1.5, 3, 6, 12, and 24 months after treatment completion.

8.6 Trismus Assessment

Trismus or restricted mouth opening is a very common side effect after conventional radiation therapy for nasopharyngeal carcinoma. Radiotherapy involving the structures of the temporomandibular joint or muscles of mastication could result in trismus. The degree of trismus will be measured by serial changes of the maximal inter-incisal distance in the vertical opening, right lateral, and left lateral jaw movements. The trismus assessment will be conducted within 14 days of initiation of radiation treatment and at 1.5, 3, 6, 12, and 24 months after treatment completion.

8.7 Patient Swallowing Diary

Besides the objective assessment of swallowing function by the videofluoroscopic measurements, patient self-assessment of swallowing function is also important. Subjective swallowing dysfunction has been shown to be common after conventional radiation therapy for nasopharyngeal carcinoma (16). In the patient swallowing diary, patients will be ask about their swallowing function with solids and liquids before radiation begins, each day during radiation treatment, and at 1.5, 3, 6, 12, and 24 months after treatment completion.

9.0 Data Collection

Table 13. Evaluations before, during, and after chemoradiation

	Pre-study (timing before study entry)	Pre-treatment	During chemoradiation^b	During chemotherapy alone	Follow-up^c
History & physical	14 days		X	X	X
Disease	8 weeks				X

Version 2.0

Date: 6.21.2011

-

documentation	(*EUA)				
Dental evaluation		6 months			
Tobacco and alcohol assessment		14 days			
Nutritional evaluation		1 month			
Patient swallowing diary		14 days	X		1.5, 3, 12, 24 months ⁱ
CBC/platelets	14 days		X	X ^h	X
Chemistry (alkaline phosphatase ^a , AST, ALT, bilirubin, BUN, serum creatinine, creatinine clearance (if indicated), electrolytes (Na, K, Mg, Cl), calcium, protein, albumin, urinalysis (if indicated))	14 days		X (Weekly for BUN and creatinine. Every 3 weeks for the others)	X (Every 3 weeks)	
β-HCG for females at risk for pregnancy	14 days				
Thyroid function panel (TSH, T3, T4)	14 days				X ^l
Chest X-ray or CT	1 month				X ^d
CT/MRI of H&N	1 month				X ^d
PET/CT ^f		1 month			X
Toxicity evaluation			X	X ^c	X
Swallow study		21 days			3, 12, 24 months ⁱ
Salivary study		21 days			3, 6, 12, 24 months ⁱ
Speech assessment (HNHSAI)		14 days			1.5, 3, 6, 12, 24 months ⁱ
Subjective QOL		14 days			1.5, 3, 6, 12, 24 months ⁱ
Physician dysphagia log		14 days			1.5, 3, 6, 12, 24 months ⁱ

Audiogram	6 weeks				X ^g
Chemosensory questionnaire (CSQ)		14 days			1.5,3,6,12,24 months ⁱ
Trismus assessment		14 days			1.5,3,6,12,24 months ⁱ

* EUA = examination under anesthesia

X denotes the type of evaluation that needs to be performed during the study period.

- a. Liver CT or MRI must be done in presence of elevated alkaline phosphatase, AST, or bilirubin or other clinical indicator; bone scan must be done in presence of elevated alkaline phosphatase or other clinical indicator.
- b. Weekly during radiotherapy.
- c. Follow-up will be performed after radiation and then every 3 (+/- 3 weeks) months during the first two years; every 6 (+/- 3 months) months during years 3 - 5; then annually (+/- 6 months). After year 5, patients are encouraged to continue with the follow-up appointments and studies annually (+/- 6 months). All follow-up appointments and studies may be performed at non-participating institutions with results sent to the participating institutions for review.
- d. These tests will be performed at least every 6 months (+/- 3 months) during the first 3 years; the first CT/MRI of nasopharynx will be performed at approximately 2 months after radiation.
- e. Prior to each cycle.
- f. PET/CT is optional but encouraged. It will be performed prior to treatment (must be ≤ 21 days prior to study entry), at approximately 2 months after radiation, and every 6 months during the first 3 years.
- g. Yearly (+/- 6 months) or clinically indicated. Once patients have reached the 24-month follow-up time point, patients are encouraged but not required to perform these studies at their annual (+/- 6 months) follow-up appointments.
- h. Every three weeks, or more frequently as clinically indicated. CBC/platelets must be drawn before treatment, either on day 1 of each cycle or no more than 72 hours in advance of each cycle.
- i. The 1.5 month studies will be performed at 1.5 (+/- 1) month after radiation, 3-month studies will be performed at 3 months (+/- 6 weeks), the 6-month studies will be performed at 6 (+/- 3) months, the 12-month studies will be performed at 6 (+/- 3 months), and the 24-month studies will be performed at 24 (+/- 6) months. Once patients have reached the 24-month follow-up time point, Patients are encouraged but not required to perform these studies at their annual (+/- 6 months) follow-up appointments.

10.0 Adverse Events Reports

Version 2.0

Date: 6.21.2011

-

Adverse events resulting from unanticipated treatment toxicity that is life threatening or fatal will be reported to the IRB within 10 working days.

11.0 Modality Review

Local Recurrence

Local recurrence is defined as: evidence of tumor growth/regrowth in any direction beyond that present on the pre-treatment imaging studies or the appearance of tumor in tissues previously scored as sites of sub-clinical disease. The imaging studies are to be comparable in technical factors. Site of failure will be related to treatment volumes PTV1, 2, and 3.

Nodal Recurrence

Recurrence in regional draining lymph nodes

Compliance to therapy

Defined as the number of courses of concurrent and adjuvant chemotherapy received, as well as the time required to complete the radiotherapy.

Distant Recurrence

Defined as appearance of tumor at sites beyond regional nodal and marginal sites.

Progression-Free and Overall Survival

Measured from the date of registration to the date of progressive disease or death.

12.0 Biostatistical Considerations

The rationale of using protons in the combined modality treatment of locally advanced nasopharyngeal carcinoma is the potential to improve patient outcome if the treatment compliance were improved by reducing acute toxicity. In particular, better tolerance of systemic chemotherapy is expected with the greater degree of normal tissue sparing by the proton beam. Only 55% of the patients on the Intergroup Study completed all 3 concurrent and 3 adjuvant cycles of chemotherapy (9), using the same regimen as in the present protocol. A sample size of 25 patients will provide 80% power to determine an increase in the chemotherapy completion rate to at least 77% at a one-sided significance level of 6%. The error rates correspond to a decision rule that requires a minimum of 18 patients to complete all 6 cycles of protocol-indicated chemotherapy.

Mucositis was the most common reason for discontinuing chemotherapy in the Intergroup study, with 37% of patients experiencing grade 3 or 4 events on the chemoradiation arm. If grade 3 or 4 mucositis were observed among no more than 5 of the 25 patients treated by proton radiotherapy, 80% power will be available to detect a decrease in the rate to 16%. The decision rule is associated with a one-sided significance

Version 2.0

Date: 6.21.2011

-

level of 6% under the null hypothesis assuming no difference from the Intergroup data. In general, 25 patients will provide 90% confidence interval widths that are no more than 35% for estimating the rate of acute and late effects. As all other toxicities are expected to be less common than mucositis, interval widths will be much narrower in practice.

A secondary objective will investigate the rate and pattern of loco-regional recurrence. In addition to progression-free survival, the rate of loco-regional failure first will be estimated by allowing for competing risks due to distant failure and death from other causes. The subgroup sample size will be limited for each of the T1-T2 and T3-T4 tumor categories, especially as the patient distribution cannot be projected definitively for the accrual of only 25 patients with a rare cancer. Thus the goal will be mainly to show the null hypothesis cannot be rejected, that is, the local control rate in tumor subgroups will not be lower than that observed using conventional radiotherapy in combined modality treatment. The accrual goal of 25 patients is anticipated to be reached in about 3 years. The referral pattern of tumor stage to proton treatment suggests the expected accrual distribution will be approximately 6 patients with T1 - 2 tumors and 18 patients with T3 - 4 tumors. Assuming the local-regional control rate was 70% for T1-T2 tumors at 3 years based on conventional radiotherapy regimens, the probability is 7% for at least 4 of 6 patients to have experienced local-regional failure within 3 years. If the local-regional control rate of T3 - 4 tumors using protons were the same as the historical 50% rate using conventional radiotherapy, the probability is 5% for 13 or more of 18 patients to have failed locally or in the regional lymph nodes.

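### Secondary objective: failing to reject the null in about 6 T1-2 and 18 T3-4 patients does not show that local control is no lower, and the 70% and 50% benchmarks have no source

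*Combined protocol and SAP*

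**What the plan says.** The last paragraph of section 12.0 (Biostatistical Considerations) covers the secondary objective. It plans progression-free survival and a competing-risks analysis: "the rate of loco-regional failure first will be estimated by allowing for competing risks due to distant failure and death from other causes". It admits that the T subgroups will be small and then states the aim: "Thus the goal will be mainly to show the null hypothesis cannot be rejected". The same sentence explains what that would mean: "that is, the local control rate in tumor subgroups will not be lower than that observed using conventional radiotherapy in combined modality treatment".

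The expected split is "approximately 6 patients with T1 - 2 tumors and 18 patients with T3 - 4 tumors". Two probabilities follow:

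- **T1-2.** Control is assumed to be a rate that "was 70% for T1-T2 tumors at 3 years based on conventional radiotherapy regimens". The chance of at least 4 failures in 6 is given as 7%.
- **T3-4.** Control is taken as "the same as the historical 50% rate using conventional radiotherapy". The chance of 13 or more failures in 18 is given as 5%.

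The paragraph gives no probability at any lower control rate, no non-inferiority margin, and no confidence interval for the competing-risks estimate. Neither benchmark has a reference.

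**The concern.** The sentence treats absence of evidence of harm as evidence of no harm. A test that does not reject supports a claim of no loss only if it would probably have rejected had a loss of concern been present. The plan never addresses that probability. It also gives the small subgroups as the reason for choosing this goal, although small numbers make non-rejection less informative.

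The benchmarks add a second difficulty. The goal names conventional radiotherapy within combined-modality treatment as the comparator, whereas the two rates are described only as coming from conventional radiotherapy. If they reflect radiotherapy alone, the bar may be too low for a chemoradiation trial. The text does not settle which is meant.

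At stake is a published statement that tumor control with protons is no worse, made from data that are also compatible with a substantial loss.

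**Working it through.** **Inputs** (all from section 12.0): n = 6, benchmark control 70% (failure 30%), count 4; n = 18, benchmark control 50% (failure 50%), count 13. Failures X are taken as binomial with every patient's 3-year status known.

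**1. The plan's own figures.**

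- P(X ≥ 4 | 6, 0.30) = 0.0595 + 0.0102 + 0.0007 = 0.0705, stated as 7%.
- P(X ≥ 13 | 18, 0.50) = 0.0481, stated as 5%.

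Both reproduce. They are the chances of a false alarm when control equals the benchmark.

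**2. Chance of not reaching the count when control is truly lower.** This is P(X ≤ 3 | 6, 1 − c) for T1-2 and P(X ≤ 12 | 18, 1 − c) for T3-4, where c is true control.

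| Group (benchmark) | True control | Count reached | Not reached |
|---|---|---|---|
| T1-2 (70%) | 60% | 18% | 82% |
| T1-2 (70%) | 50% | 34% | 66% |
| T1-2 (70%) | 40% | 54% | 46% |
| T3-4 (50%) | 40% | 21% | 79% |
| T3-4 (50%) | 33% | 41% | 59% |
| T3-4 (50%) | 30% | 53% | 47% |
| T3-4 (50%) | 25% | 72% | 28% |

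**3. Loss needed for a reliable signal.** Solving P(X ≥ 4 | 6, 1 − c) = 0.80 gives c = 0.269. Solving P(X ≥ 13 | 18, 1 − c) = 0.80 gives c = 0.225. True control must therefore fall from 70% to about 27%, or from 50% to about 22%, before the counts are reached with 80% probability.

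**4. Worst results that stay below the counts** (exact Clopper-Pearson 90% intervals for control).

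- 3 failures in 6: control 50%, interval 15% to 85%; the estimate is 70 − 50 = 20 points below benchmark.
- 12 failures in 18: control 33%, interval 16% to 55%; the estimate is 50 − 33 = 17 points below benchmark.
- At the other extreme, 0 failures in 6 gives a lower limit of 61%, still under 70%. No T1-2 result at this size can exclude control below the benchmark.

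**5. Precision.** The widest exact 90% interval is 69 points for n = 6, 42 for n = 18 and 35 for n = 25. The last agrees with the plan's statement on acute and late effects that "25 patients will provide 90% confidence interval widths that are no more than 35" percentage points. The subgroups have nothing close to that precision.

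**6. Benchmarks.** The nearest background figures are in section 1.1: local control with conventional once-daily radiation of 75% or higher for Stage I-II and 20% to 70% for Stage III-IV. These are by overall stage, not T category. They do not yield 70% for T1-2, and 50% is one point in a wide range. The tail probabilities depend on the choice: P(X ≥ 4 of 6) is 7.0% at a 70% benchmark and 3.8% at 75%; P(X ≥ 13 of 18) is 4.8% at 50%, 0.03% at 70% and 87% at 20%.

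**The case against.** The strongest reply is that the plan is mainly about estimation. Section 2.2 asks only for the rate and pattern of locoregional recurrence, section 12.0 plans a competing-risks estimate, and it discloses the small subgroups. It uses the term decision rule for both primary criteria but not for the 4-of-6 and 13-of-18 counts, which can be read as describing what would be surprising. The 70% is introduced as an assumption, and conventional radiotherapy may be shorthand for the combined-modality comparator named earlier in the paragraph.

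Much of this stands. The miss probabilities depend on reading the counts as thresholds, and the comparator mismatch is an ambiguity, not a demonstrated error. Non-rejection is also not the likelier result for every loss: at 30% T3-4 control or 40% T1-2 control the counts are reached slightly more often than not. The exact binomial widths show scale only, because intervals for a cumulative incidence under censoring will differ.

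None of it rescues the sentence. The equation of non-rejection with control being no lower is explicit, and it is wrong whatever thresholds are used. Admitting that the subgroups are small and then drawing the stronger conclusion does not make that conclusion valid.

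**Conclusion.** The concern holds. The stated inference is wrong as written, not merely under-specified. The plan's arithmetic is right; the fault is in what it is taken to show. With the counts read as thresholds and complete 3-year follow-up assumed, a 20-point loss of control would go unflagged 66% of the time in T1-2 and 47% in T3-4, and a 10-point loss 82% and 79% of the time.

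The missing source for the benchmarks is a lesser point; alone it would be a request for detail. The issue should be fixed, but it is confined to a secondary objective: the chemotherapy-completion and mucositis rules and the sample size of 25 do not depend on it.

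**What to change.** - Delete the goal of showing that the null cannot be rejected, and the conclusion that control is no lower.
- Report the competing-risks estimate of 3-year locoregional failure, already planned, with 90% confidence intervals for all patients, and descriptively by T group.
- If the 4-of-6 and 13-of-18 counts are kept, label them as harm signals only and print the probability of reaching them at lower true control: for T3-4, 21% at 40% control and 53% at 30%; for T1-2, 34% at 50% control.
- Give a source for the 70% and 50% from combined-modality treatment, or state that they come from radiotherapy alone.

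The cost is rewording one paragraph and a few binomial calculations, with no design change. The price is a weaker statement on tumor control: the subgroup intervals will be wide, and for about 6 T1-2 patients close to uninformative, which is what the data can support.

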1.0 Background and Significance

1.1 Background

In the USA and Western Europe, nasopharyngeal carcinoma (NPC) accounts for less than 1% of malignancies. The average incidence increases 80-fold in endemic areas such as Southern China. NPC is a neoplasm that differs from other squamous cell carcinomas of the head and neck with regard to epidemiology, histologic features, treatment strategies, and treatment response. Due to the anatomical location, nasopharyngeal cancers are considered unresectable. The conventional treatment approach has been radiation. Local control rates with conventional once daily radiation are 75% or higher for Stage I and II diseases but decrease to 20 - 70 % for Stage III and IV diseases. For patients with advanced NPC (stage III - IV) treated with radiation alone, the 5-year survival rates are only 10 - 40% (1 - 7).

The predominant patterns of failure for locally advanced NPC are local recurrence and distant metastasis. In a retrospective analysis of 1301 patients with NPC, locoregional recurrence was shown to be an independent prognostic indicator of subsequent distant metastases (8). Achieving local control is therefore important in the treatment of nasopharyngeal carcinoma.

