1.2 Combined radiation and chemotherapy is superior to radiotherapy alone

The standard of care of treatment in the United States is concurrent chemoradiation followed by adjuvant chemotherapy, based on the results of the Intergroup study (SWOG/RTOG/ECOG), which showed improved progression-free and overall survival with chemoradiation compared with radiation alone (9). The study compared radiotherapy (70 Gy) alone to chemotherapy concurrent with radiotherapy followed by adjuvant chemotherapy in patients with nasopharyngeal cancer. This revealed a statistically significant increase in 3-year progression-free survival (69% versus 24%) and 3-year overall survival (76% versus 46%) in favor of the chemoradiotherapy arm. Lin et Al recently reported increased progression-free and overall survival rates in patients who received 2 cycles of continuous cisplatin and fluorouracil chemotherapy during radiotherapy compared to radiotherapy alone in patients with locally advanced nasopharyngeal carcinoma in endemic areas (10). Chan et al in a randomized trial of 350 patients, showed that patients who received weekly cisplatin of 40 mg/m² during radiation had a prolonged progression-free survival compared to patients who received radiation alone (11). These studies suggest that concurrent chemoradiation with or without adjuvant chemotherapy is superior to radiotherapy alone in patients with locally advanced NPC in endemic and non-endemic areas.

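### The T3-4 locoregional benchmark of 50% is not shown to be a chemoradiation rate, although the stated comparison is with combined modality treatment, and it makes the 13-of-18 threshold very lenient

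*Combined protocol and SAP*

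**What the plan says.** Section 12.0 states the aim for the T-category subgroups as showing that "the local control rate in tumor subgroups will not be lower than that observed using conventional radiotherapy in combined modality treatment". Two reference rates follow, each with a tail probability.

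- **T1-2:** a 7% chance of four or more failures among six patients, under this premise: "Assuming the local-regional control rate was 70% for T1-T2 tumors at 3 years based on conventional radiotherapy regimens".
- **T3-4:** a 5% chance of at least 13 failures among 18 patients, under this premise: "If the local-regional control rate of T3 - 4 tumors using protons were the same as the historical 50% rate using conventional radiotherapy".

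The expected accrual is about 6 patients with T1-2 and 18 with T3-4 tumours. Neither rate carries a citation or says whether the patients behind it had chemotherapy.

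Two background figures bear on this. Section 1.1, describing conventional once-daily radiation, gives local control of "75% or higher for Stage I and II diseases but decrease to 20 - 70 % for Stage III and IV diseases". Section 1.2 gives three-year PFS in the Intergroup study of 69% with chemoradiation and 24% with radiotherapy alone. Section 12.0 describes the Intergroup chemotherapy as the same regimen as in this protocol and uses that study as the reference for both primary rules.

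**The concern.** The comparator named in the aim is chemoradiation with conventional radiotherapy. The T3-4 rate is described only as a historical rate with conventional radiotherapy, and 50% lies inside the range that section 1.1 gives for radiation in Stage III-IV disease. If the 50% comes from radiotherapy without chemotherapy, the threshold answers a different question from the one stated: whether protons with chemotherapy do worse than radiotherapy alone.

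This matters because the plan intends to rest its conclusion on not rejecting the null. With a reference rate that is too low, non-rejection is nearly guaranteed. As written, 12 locoregional failures among 18 T3-4 patients, which is 33% control (6/18), would not reach the threshold and could be reported as not lower than combined modality treatment.

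**Working it through.** **1. The plan's own figures.** Exact binomial upper tails:

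- T1-2: P(X ≥ 4 | n = 6, failure 0.30) = 0.0705, stated as 7%.
- T3-4: P(X ≥ 13 | n = 18, failure 0.50) = 0.0481, stated as 5%.

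Both reproduce. The arithmetic is right; the question is the input.

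**2. A floor from section 1.2.** Assume that locoregional recurrence counts as progression. A patient who is progression-free at three years then has had no locoregional failure, so three-year locoregional control is at least three-year PFS. On the Intergroup chemoradiation arm, pooled over T categories, that is at least 69%. The 69% is taken at face value.

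**3. Do the two reference rates meet the floor?** Let w be the T1-2 share.

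- Pooled control = 0.70w + 0.50(1 − w).
- At this trial's mix, w = 6/24 = 0.25, it is 0.175 + 0.375 = 0.55, which is 14 points below 69%.
- Reaching 0.69 needs w ≥ (0.69 − 0.50)/0.20 = 0.95.

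Taking the 50% alone and letting T1-2 control be c, the requirement is w ≥ 0.19/(c − 0.50). With c = 1.00 this is 38%; with c = 0.90 it is 47.5%; with c = 0.80 it is 63%.

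The 70% for T1-2 does not conflict with the floor. Moving it to 69% changes its tail only from 7.0% to 7.9%.

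**4. The implied floor for T3-4.** The Intergroup T mix is not in the documents. Assuming the 25/75 mix expected here, the T3-4 floor is (0.69 − 0.25c)/0.75. The table gives the true level of the present threshold at that floor, the smallest cut-off in 18 with level 5% or less, and the probability that this cut-off is reached if true control is 50%.

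| Assumed T1-2 control c | T3-4 floor | Level of ≥ 13 of 18 | Cut-off (level) | Power at 50% control |
|---|---|---|---|---|
| 100% | 58.7% | 0.8% | ≥ 12 (2.7%) | 11.9% |
| 90% | 62.0% | 0.3% | ≥ 11 (4.0%) | 24.0% |
| 70% | 68.7% | 0.04% | ≥ 10 (2.8%) | 40.7% |

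The present threshold is reached 4.8% of the time at 50% control, by construction. The loss is therefore about 7 points (11.9 − 4.8), 19 points (24.0 − 4.8) or 36 points (40.7 − 4.8).

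**5. A pooled alternative.** With failure 0.31 and all 25 patients, P(X ≥ 12) = 0.056. At failure 0.50 it is 0.655.

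**The case against.** Several points on the other side stand.

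- **Wording.** The protocol often uses the word conventional to mean non-proton, and the aim itself speaks of conventional radiotherapy within combined modality treatment. The later phrases could be shorthand for that. Section 1.1 is weak evidence of origin: it reports by stage rather than T category, its Stage III-IV range is wide, and the plan's 70% for T1-2 lies below the 75% given there for Stage I-II. Origin in radiation alone is a strong inference, not a stated fact.
- **Compatibility.** A reader might infer that the reference rates cannot be chemoradiation rates. The documents do not show this, because they do not give the Intergroup T mix. Nor do they support faulting both rates: only the 50% creates the tension.
- **Size.** A reader might take 69% as the T3-4 chemoradiation rate and quote only the 36-point loss. But 69% is a pooled floor, and the plan itself expects T3-4 control to be lower than T1-2. The documents give no T3-4 chemoradiation rate, so the size is a range.
- **Purpose.** A reader might link this objective to loss of target coverage, since section 6.4.4 ranks normal-structure constraints above dose specifications. Section 2.2 speaks only of the rate and pattern of recurrence.
- **Weight.** Section 12.0 attaches no action to these thresholds, acknowledges that the subgroups are small, and plans competing-risks estimation, which does not depend on the benchmark.

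These points narrow the concern but do not remove it. Reading the phrase as shorthand leaves a 50% rate that sits uneasily with the 69% PFS. At the assumed 25/75 mix the direction is the same for every T1-2 control rate considered.

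**Conclusion.** The concern holds in a limited form. The comparator named in the aim and the description of the 50% T3-4 rate do not match. At this trial's expected mix, the two reference rates together fall 14 points short of the floor implied by the protocol's own chemoradiation PFS. Against a T3-4 floor of about 59% to 69%, the 13-of-18 threshold operates at 0.8% to 0.04% rather than 5%. A realigned cut-off would have 12% to 41% power if true control were 50%, against 4.8% now.

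This rests on three assumptions: that locoregional recurrence counted as progression in the Intergroup study, that its T mix resembled 25/75, and that T1-2 control there lay between 70% and 100%. With a T1-2 share of 38% or more, a 50% T3-4 rate could be compatible, but at 38% only if T1-2 control were 100%.

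Only the secondary objective is affected. The sample size of 25 and the rules for chemotherapy completion and mucositis stand. It should be corrected, because the text as written permits a claim about combined modality treatment that the benchmark may not support.

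**What to change.** In section 12.0, state the source of the 50% T3-4 rate and whether those patients received chemotherapy. If they did not, do one of the following:

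1. Replace it with a three-year T3-4 locoregional control rate from photon chemoradiation, and recompute the threshold for 18 patients.
2. Keep the 50%, name radiotherapy alone as the comparator for T3-4, and do not describe the result as not lower than combined modality treatment.

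Giving the source of the 70% T1-2 rate at the same time would be sensible, but no conflict requires it to change.

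A pooled benchmark of at least 69% control could be added as a supplementary check: 12 or more failures in 25, exact level 5.6%, power 65% if true control is 50%. It should not replace the T-category thresholds. It borrows PFS, a different endpoint, from an arm of unknown T mix, so a flag could reflect case mix rather than protons.

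The cost is some wording and a few binomial figures, with no extra patients or data. The downside is a stricter benchmark, which the trial is more likely to miss, or a narrower claim.
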